7.4 CONCOMITANT THERAPY

For this protocol, a prescription medication is defined as a medication that can be prescribed only by a properly authorized/licensed clinician. Medications to be reported in the Case Report Form (CRF) are concomitant prescription medications, over-the-counter medications and supplements.

8. STUDY INTERVENTION DISCONTINUATION AND PARTICIPANT DISCONTINUATION/WITHDRAWAL

8.1 SUSPENSION OF STUDY INTERVENTION

In this section, study “pause” indicates that immunizations will be briefly stopped for a particular group to allow consultation with the Sponsor and DSMB. Immunizations may resume immediately based on (1) the decision of the Sponsor, taking into account any recommendations of the DSMB and (2) concurrence by the principal investigator. IRBs and regulatory authorities will be notified but need not be involved in the decisions. Alternatively, if a study has been paused, the Sponsor may decide to impose a “safety hold,” implying the need for wider consultation, potentially including IRBs and regulatory agencies, depending on the circumstances. A pause or a safety hold may be restricted to a particular subgroup, depending on the circumstances.

The study intervention will be paused if specified criteria in **Section 7.1.1** are met (see below). Discontinuing vaccinations does not mean discontinuation of study visits or procedures related to safety. Study procedures related to research assays, such as collecting samples for immunology tests, may be continued if participants and their parents/guardians agree.

- Five percent or more of the vaccinees enrolled at any time point in one arm (calculated as 5% of the vaccinees in the full study roster enrolled to date, as long as there are at least three subjects with the AE) experience the same severe (grade 3) AE during the periods of AE collection deemed possibly, probably or definitely related to study product administration (PfSPZ Vaccine or NS), or experience the same grade 3 laboratory abnormality on day V2 + 14 or day V3+14. Grade 3 AEs deemed possibly, probably or definitely related to malaria (as opposed to PfSPZ Vaccine or to NS) will not count toward meeting this criterion. The site, where clinical staff are blinded, can only monitor total populations (vaccine plus placebo recipients) and if a 5% threshold is reached, unblinded study staff (e.g., the head of Pharmaceutical Operations) will need to confirm that the total indeed constitutes 5% of vaccinees. Note that we have considered using Grade 2 rather than Grade 3 laboratory abnormalities, but drops in hemoglobin, neutrophils, platelets and sometimes other blood count indices meeting Grade 2 criteria for severity are common in African pediatric populations.
- One participant experiences an SAE deemed possibly, probably or definitely related to study product. This criterion will not be met if it turns out that the participant received NS. SAEs related to malaria or to antimalarial treatment which are expected, will be reported expeditiously but will not fulfill this criterion. If the SAE is unexpected with respect to malaria or antimalarial treatment, it will fulfill the criterion.

If either of these criteria appear to be met by ongoing surveillance at the site, the principal investigator will engage the head of Pharmaceutical Operations on site, or his/her designee, to

follow unblinding procedures (see **Section 6.3.3** for a description). To meet the criteria, the subjects must actually have received PfSPZ Vaccine and not NS placebo.

After confirmation that a pausing criterion has been met, the Sponsor will contact the DSMB to describe the circumstances of the event(s). After an email discussion or, if recommended by the DSMB, an ad hoc teleconference, the DSMB, which will include the local safety monitor as a voting member, will make a written recommendation about whether or not the study should be unpause, remain paused pending more data and further review, or placed on full safety hold, and whether or not the affected participants or their caregivers should be unblinded and notified of their treatment assignment. Based on the DSMB recommendation, a decision will be made by the Sponsor and principal investigator to either unpause the study and continue administration of investigational product in the affected group, to pause the study temporarily in the affected group to allow collection of more data about the triggering event(s) or other safety data, or to institute a full safety hold for the affected group or groups. IRBs (excepting IRBs providing administrative review) and regulatory authorities will be promptly informed of a study pause or of a full safety hold. Their permission will not be required to un-pause the study, but will be to reverse a safety hold.

Irrespective of the pausing criteria, the Sponsor, local safety monitor, principal investigator or applicable ethical committees or regulatory agencies may decide to pause the study, or to put the study on safety hold based on any constellation of AEs even if the 5% threshold is not reached and even if the AEs do not reach Grade 3 severity, or based on any other legitimate reason, such as AEs occurring in another study, product quarantine, manufacturing issues, expiry of permissions, out-of-specification stability test results, etc. For a full safety hold to be lifted, there must be written concurrence by the entity or entities that initiated the hold that the study can resume, and this may include regulatory agencies in addition to the two IRBs of record.

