9.11.2 Definition of Serious Adverse Events (SAE)

An adverse event (AE) or suspected adverse reaction is considered "serious" if, in the view of either the investigator or sponsor, it results in any of the following outcomes:

- death,
- a life-threatening adverse event,
- inpatient hospitalization or prolongation of existing hospitalization,
- a persistent or significant incapacity or substantial disruption of the ability to conduct normal life functions, or

Important medical events that may not result in death, be life-threatening, or require hospitalization may be considered serious when, based upon appropriate medical judgment, they may jeopardize the participant and may require medical or surgical intervention to prevent one of

the outcomes listed in this definition. Examples of such medical events include allergic bronchospasm requiring intensive treatment in an emergency room or at home, blood dyscrasias or convulsions that do not result in inpatient hospitalization.

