9.11.3 Classification of an Adverse Event

Severity of Event

For adverse events (AEs) not included in the protocol defined grading system (see Appendix A), the following guidelines will be used to describe severity.

- **Mild** – Events require minimal or no treatment and do not interfere with the participant’s daily activities.
- **Moderate** – Events result in a low level of inconvenience or concern with the therapeutic measures. Moderate events may cause some interference with functioning.
- **Severe** – Events interrupt a participant’s usual daily activity and may require systemic drug therapy or other treatment. Severe events are usually potentially life-threatening or incapacitating. Of note, the term “severe” does not necessarily equate to “serious”.]

Relationship to Study Intervention

All adverse events (AEs) must have their relationship to study intervention assessed by the investigator who examines and evaluates the participant based on temporal relationship and his/her clinical judgment. The degree of certainty about causality will be graded using the categories below. In a clinical trial, the study product must always be suspect.

- **Definitely Related** – There is clear evidence to suggest a causal relationship, and other possible contributing factors can be ruled out. The clinical event, including an abnormal laboratory test result, occurs in a plausible time relationship to study intervention administration and cannot be explained by concurrent disease or other drugs or chemicals. The response to withdrawal of the study intervention (dechallenge) should be clinically plausible. The event must be pharmacologically or phenomenologically definitive, with use of a satisfactory rechallenge procedure if necessary.
- **Probably Related** – There is evidence to suggest a causal relationship, and the influence of other factors is unlikely. The clinical event, including an abnormal laboratory test result, occurs within a reasonable time after administration of the study intervention, is unlikely to be attributed to concurrent disease or other drugs or chemicals, and follows a clinically reasonable response on withdrawal (dechallenge). Rechallenge information is not required to fulfill this definition.

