9.11.4 Time Period and Frequency for Event Assessment and Follow-Up

The occurrence of an adverse event (AE) or serious adverse event (SAE) may come to the attention of study personnel during study visits and interviews of a study participant presenting for medical care, or upon review by a study monitor.

All AEs including local and systemic reactions not meeting the criteria for SAEs will be captured on the appropriate case report form (CRF). Information to be collected includes event description, time of onset, clinician's assessment of severity, relationship to study product (assessed only by those with the training and authority to make a diagnosis), and time of resolution/stabilization of the event. All AEs occurring while on study must be documented appropriately regardless of relationship. All AEs will be followed to adequate resolution.

Any medical condition that is present at the time that the participant is screened will be considered as baseline and not reported as an AE. However, if the study participant's condition deteriorates at any time during the study after enrollment, it will be recorded as an AE.

Changes in the severity of an AE will be documented to allow an assessment of the duration of the event at each level of severity to be performed. AEs characterized as intermittent require documentation of onset and duration of each episode.

At each study visit, the investigator will inquire about the occurrence of AE/SAEs since the last visit. Events will be followed for outcome information until resolution or stabilization.

If a diagnosis is clinically evident (or subsequently determined), the diagnosis rather than the individual signs and symptoms or lab abnormalities will be recorded as the AE.

All solicited (see **Table 12** below) and unsolicited AEs will be recorded through Day 7 after each injection. Injection site reactions will be assessed until Day 7 after injection (PfSPZ Vaccine or normal saline) or until resolved.

After the periods specified above only unsolicited aEs, SAEs, UPs, and new onset of chronic illness (NOCI) will be recorded.

Table 12. Solicited Adverse Events

Laboratory adverse events¹	
Hemoglobin (decreased hemoglobin)	Platelet count (thrombocytopenia or thrombocytosis)
WBC (leukopenia or leukocytosis)	Creatinine (Cr) (increased Cr)
ANC (neutrophil count decreased) or AGC (granulocyte count decreased)	ALT (increased ALT)

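### The first pausing criterion names Grade 3 without 'or higher', so Grade 4 laboratory values, and creatinine above 200 without dialysis, do not count as written

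*Protocol*

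**What the plan says.** Protocol 8.1 makes the pause mandatory once a criterion in 7.1.1 Pausing Criteria, Unblinding and Safety Hold is met. The first criterion needs 5% or more of the vaccinees enrolled to date, and at least three subjects. It has two limbs:

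- a clinical limb, for vaccinees who "experience the same severe (grade 3) AE during the periods of AE collection" that is judged at least possibly related to study product;
- a laboratory limb, "or experience the same grade 3 laboratory abnormality on day V2 + 14 or day V3+14", which carries no relatedness condition.

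An exclusion follows: "Grade 3 AEs deemed possibly, probably or definitely related to malaria" are left out of the count. The same paragraph explains the laboratory cut-off: "Note that we have considered using Grade 2 rather than Grade 3 laboratory abnormalities". Grade 2 was rejected because blood-count falls of that size are common in African children.

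The second criterion is a single SAE at least possibly related to study product. The section also lets the sponsor, the investigator and other named parties pause at their discretion, "even if the AEs do not reach Grade 3 severity".

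Appendix A gives every laboratory test a Grade 4 column separate from Grade 3.

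**The concern.** A pausing rule is run as a count. Blinded staff tally events, and the head of Pharmaceutical Operations confirms how many belong to vaccinees. Both limbs and the exclusion name one grade, and no other text in the protocol or SAP adds Grade 4 to the count. The protocol does use or-higher wording elsewhere: Table 9 has creatinine and other rows labelled that way. Taken literally, a child whose result worsens from Grade 3 to Grade 4 leaves the tally, and a cluster made up only of Grade 4 values would never meet the laboratory limb, whatever its size.

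Timing decides where this matters. The V2 + 14 sample is the last safety laboratory check before third doses. The protocol asks for particular care after dose two, because this is only the second paediatric study of two priming doses a week apart.

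**Working it through.** **1. Grade boundaries (Appendix A, Mali Laboratory AE Grading for Pediatric Population)**

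| Test | Grade 3 | Grade 4 | Relation |
|---|---|---|---|
| Hemoglobin, g/dL | 5.0–6.0 | <5.0 | disjoint |
| WBC increase, 10³/µL | 20.1–30.0 | >30.0 | disjoint |
| WBC decrease, 10³/µL | 1.0–1.4 | <1.0 | disjoint |
| Neutrophils, 10³/µL | <0.50 | <0.50 with fever | overlap |
| Platelets, 10³/µL | 25–69 | <25 | disjoint |
| Creatinine, µmol/L | 150.00–200.00 | >200.00 plus need for dialysis | gap |
| ALT, U/L | 301.0–600.0 | >600.0 | disjoint |

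Five of the seven rows are disjoint, one overlaps and one has a gap. Footnote 2 to the table also allows a value in a Grade 3 range to be recorded as Grade 4 when signs or symptoms accompany it, which moves it out of the count as worded.

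**2. Creatinine.** Applying the row: 160 and 200 are Grade 3; 400 with dialysis is Grade 4; 201 or 400 without dialysis has no grade. Inserting *or higher* in the criterion does not reach these values, so the row needs its own correction. Footnote 1 calls the values guidelines, and 9.11.3 has a fallback scale ("For adverse events (AEs) not included in the protocol defined grading system"), but neither assigns this value a grade.

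**3. Trigger count.** Trigger = max(3, 0.05 × vaccinees rounded up).

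- 134 vaccinees (planned arm): 0.05 × 134 = 6.7, so 7.
- 60 vaccinees: 0.05 × 60 = 3, so 3.

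**4. Effect on the count, same laboratory abnormality**

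| Vaccinees | Grade 3 | Grade 4 | As worded | With *or higher* |
|---|---|---|---|---|
| 134 | 6 | 1 | 6/134 = 4.5%, not met | 7/134 = 5.2%, met |
| 134 | 0 | 7 | 0/134, not met | 7/134 = 5.2%, met |
| 60 | 2 | 1 | 2/60 = 3.3%, not met | 3/60 = 5.0%, met |

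**5. Timing (Schedule of Activities).** V2 is Day 8, so V2 + 14 is Day 22. V3 is Day 29, nominally 29 − 22 = 7 days later, so a pause at Day 22 can still withhold third doses. V3 + 14 is Day 43, when the child's own series is complete and a pause protects only children not yet fully dosed.

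**6. What the documents say about frequency.** Table 9 (blinded Gabon trial, 36 + 101 + 63 = 200 children) lists 1 + 2 + 0 = 3 Grade 3 and 0 + 0 + 1 = 1 Grade 4 platelet falls, with no child having more than one abnormality of a given type. A Grade 4 value can therefore be recorded without a recorded Grade 3 value in the same child. All four falls were seen 1 day after injection and were normal on retest at 4 to 6 days, so they would not appear on V2 + 14 or V3 + 14. They give no rate for this gap.

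**The case against.** The strongest reply is that Grade 3 is plainly a floor. The protocol weighs Grade 2 against Grade 3 as a cut-off and speaks of events that do not reach Grade 3. Setting values aside for being too severe is a reading nobody may apply. That is probably the intent, but it argues for correcting the wording, because a count rule should not rest on inference.

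The second reply is that other routes are more sensitive. The second criterion fires at one vaccinee. Grade 4 is labelled potentially life-threatening, the SAE examples in 9.11.2 include "blood dyscrasias or convulsions that do not result in inpatient hospitalization", 9.11.3 says the study product must always be suspected, and a possible relation is enough. This narrows the gap. It does not close it: a Grade 4 laboratory value is not automatically an SAE, and the event must be judged both serious and related, whereas the laboratory limb asks for neither. The discretionary pause, and the individual hold for an abnormal laboratory value in 7.1.2 (Temporary Hold of Vaccination), can protect children, including the affected child's own V3. Neither is mandatory, and the individual hold does nothing for other children.

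The third reply concerns the clinical limb, and much of it stands. On the fallback scale nothing sits above severe. Many clinical Grade 4 cells in Appendix A involve hospitalization, which is an SAE criterion, although an ER visit alone is not. Fever above 40 °C would normally pass through the 39.0–40 band first, and "Changes in the severity of an AE will be documented". The material residue is in the laboratory limb.

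Finally, the six-plus-one example is chosen to straddle the threshold. It shows how the rule works and is not evidence of how often it would fail.

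**Conclusion.** The concern holds and is minor. As written, the first criterion does not count Grade 4 laboratory values in five of seven tests, and it does not count creatinine above 200 without dialysis, on V2 + 14 or V3 + 14. The consequence is confined to clusters near the 5% threshold, or made up largely of Grade 4 or ungraded values, that are not also judged related SAEs and do not prompt a discretionary pause. The conclusion rests on a literal reading of the rule and on the Appendix A boundaries. The threshold of 7 assumes the full planned arm of 134. The documents supply no event rates from which a probability of a missed trigger could be calculated, and none is claimed.

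**What to change.** In 7.1.1 Pausing Criteria:

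- clinical limb: *the same severe (grade 3 or higher) AE*;
- laboratory limb: *the same grade 3 or higher laboratory abnormality*;
- malaria exclusion: begin it with *Grade 3 or higher AEs*, so that malaria-related Grade 4 events are treated like malaria-related Grade 3 events.

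In Appendix A, change the Grade 4 creatinine cell so that a value above 200.00 *or* a need for dialysis qualifies.

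That is three insertions and one changed word. The 5% threshold, the minimum of three, the sampling days and the DSMB procedure stay as they are. The only operational cost is slightly more frequent contact with the DSMB.

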7.1.2 Temporary Hold of Vaccination of Individual Participants

The administration of PfSPZ Vaccine or NS to a study participant may be temporarily put on hold, based on clinical judgement, for the following reasons:

1. The participant is ill on the day of vaccination (administration may proceed in the case of a minor illness, based on the investigator's clinical judgment).
2. The participant has an abnormal laboratory value determined to be clinically significant and meriting delay in immunization, based on the investigator's clinical judgment.
3. The participant has malaria or has taken medication for malaria or for another acute illness that may affect response to PfSPZ Vaccine. Participants with malaria will be treated with an antimalarial medication and administration of PfSPZ Vaccine will be postponed for a period of time after termination of treatment that is appropriate to allow sufficient washout of the drug.
4. The participant has received a non-live vaccine during the previous 14 days or a live vaccine during the previous 28 days (other than the investigational product) or three or more of any type of vaccine in the preceding four months.
5. At the request of the participant.

6. On the advice of the principal investigator, local safety monitor, IRB, regulatory authority, DSMB or sponsor.
7. On the advice of one of the investigators, as long as the principal investigator concurs.

Vaccination will be rescheduled at the earliest possible time within the acceptable window of the originally scheduled vaccination, or outside that window if there is no other option.

8.2 DISCONTINUATION OF STUDY INTERVENTION

Discontinuation from receipt of study products (AL, PfSPZ Vaccine or normal saline) for an individual does not mean discontinuation from the study, and remaining study procedures should be completed as indicated by the study protocol. If a clinically significant finding is identified after enrollment (including, but not limited to changes from baseline), the investigator or qualified designee will determine if any change in participant management is needed. Any new clinically relevant finding will be reported as an adverse event (AE).

The data to be collected at the time of study intervention discontinuation will include continued study procedures as outlined in the protocol. If no further vaccinations are to be administered, safety labs related to vaccination schedules may be deferred at the investigator's discretion.

Participants are free to withdraw from participation in the study at any time upon request.

An investigator may discontinue or withdraw a participant from the study for the following reasons:

- Completion of study intervention
- New diagnosis which requires discontinuation of the study intervention
- If any clinical adverse event (AE), laboratory abnormality, or other medical condition or situation occurs such that continued participation in the study would not be in the best interest of the participant
- Investigator discretion
- Participant unable to receive AL dosing or subsequent vaccinations more than 7 days from proposed study window.
- Significant study intervention non-compliance
- If the participant meets an exclusion criterion (either newly developed or not previously recognized) that precludes further study participation
- Subject has completed the study follow-up period
- Death
- Screen Failure

8.3 PARTICIPANT DISCONTINUATION/WITHDRAWAL FROM THE STUDY

Participants are free to withdraw from participation in the study at any time upon request.

The reason for participant discontinuation or withdrawal from the study will be recorded on the End of Study Case Report Form (CRF). Replacement of a subject may occur in the case that a parent/guardian signs the informed consent and the subject is randomized but the subject does not go on to receive the study intervention. In the case where a parent guardian/signs the informed consent, the subject is randomized, receives the first dose of PfSPZ Vaccine and the

subject is withdrawn or the subject or parent/guardian decides to withdraw, no subject replacement may occur.

8.4 LOST TO FOLLOW-UP

A participant will be considered lost to follow-up if he or she fails to return for scheduled visits and the parent/guardian is unable to be contacted by the study site staff.

The following actions must be taken if a participant fails to return to the clinic for a required study visit:

- The site will attempt to contact the parent/guardian and reschedule the missed visit within the specified visit window and counsel the parent/guardian on the importance of maintaining the assigned visit schedule and ascertain if the parent/guardian (and if applicable, the subject) wishes to and/or should continue in the study.
- Before a participant is deemed lost to follow-up, the investigator or designee will make every effort to regain contact with the parent/guardian (where possible, 3 telephone calls and, if necessary, a home visit to the participant's last known address). These contact attempts should be documented in the participant's study file.
- Should the parent/guardian continue to be unreachable, he or she will be considered to have withdrawn the subject from the study with a primary reason of lost to follow-up.

